8.3 Survival follow-up period and survival follow-up**8.3.1 Summary statistics**

The following summaries will be provided (based on the total number of SAF patients):

- Number (%) of patients who have entered the survival follow-up following the 30-day safety follow-up visit.
- Number (%) of patients who have discontinued from the survival follow-up.
- Reasons for discontinuation from the survival follow-up.

8.3.2 Duration of overall survival follow-up

- A summary table showing the duration of follow-up will be presented for the FAS population. Summary information regarding the follow-up of patients is displayed in order to describe the maturity of data and quality of follow-up.
- Follow-up of the study will be summarized using the following metric to provide a comprehensive assessment of follow-up for patients: Follow-up time elapsed from study start reference date = (Date of event or censoring – study start reference date +

1)/30.4375 (months) regardless of censoring. Date of event or censoring is the same as the one defined in the section for overall survival analysis.

8.4 Protocol deviations

Key protocol deviation will be identified based on reviews of the data prior to database lock. Protocol deviations will be summarized overall and by center, and tabulated according to the following categories:

- Prohibited concomitant medication
- Informed consent form
- Eligibility criteria
- Laboratory assessments
- Procedure or test
- Study drug and treatment
- Visit schedule
- Other

Only protocol deviations directly affecting the patient will be reported. Protocol deviations pertaining to the study centers will not be considered. The number (%) of patients in the SAF with at least one of the above protocol deviations will be tabulated.

8.5 Baseline and demographic characteristics

Descriptive statistics will be presented for continuous variables. The number and percentage (%) of patients in each category will be presented for categorical variables. All summaries will be presented for the FAS and the SAF. For categorical variables, the number and percentage of patients with missing data will be provided. Listings for demographic data will be produced for the SAF.

The following continuous variables will be summarized:

- Age (as continuous variable [years])
- Height [cm]
- Weight [kg]
- Number of prior systemic treatment lines (DLBCL medications) as categorical variable
- Number of patients with 1 vs. ≥ 2 prior anti-DLBCL medications

STATISTICAL ANALYSIS PLAN

 MorphoSys AG
 MOR208C203

-
- BMI (calculated as weight[kg] / height[m]² using weight at baseline)
 - Time since first DLBCL diagnosis [months]
 - Time since discontinuation of last prior anti-DLBCL medication or ASCT [months]

The following categorical variables will be summarized:

- Age as categorical variable:
 - with subgroups < 65 vs. ≥ 65 years of age
 - with subgroups < 60 vs. ≥ 60 years of age
 - with subgroups < 70 vs. ≥ 70 years of age
- LDH levels at baseline (within reference range vs. beyond reference range)
- Prior ASCT (yes vs. no)
- Cell of origin (GCB vs. non-GCB based on immuno-histochemistry/central pathology)
- Cell of origin (GCB vs. ABC based on gene expression profiling)
- Rituximab refractoriness (yes vs. no)
- Refractoriness to last prior therapy (yes vs. no)
- Primary refractoriness (yes vs. no)
- ECOG
- Ann Arbor Disease Stage dichotomized (I and II vs. III and IV)
- Sex
- Race (Black or African American, American Indian or Alaskan native, Asian, Native Hawaiian or other Pacific Islander, White, Other)
- IPI score dichotomized (score 0-2 vs. 3-5, i.e., “low risk” and “low-intermediate risk” vs. “intermediate-high risk” and “high risk”)
- FcγRIIIa affinity (high affinity: FCGR3A-158V homozygosity vs. low affinity: FCGR3A-158F homozygosity, or FCGR3A-158F/V heterozygosity)
- FcγRIIa affinity (high affinity: FCGR2A-131H homozygosity vs. low affinity: FCGR2A-131R homozygosity, or FCGR2A-131H/R heterozygosity)

Note: the calculation of derived variables is described in the respective sections below.

8.6 Medical history and current medical conditions

8.6.1 Coding and definitions

Medical history and current medical conditions will be summarized by body system, preferred term and by toxicity grade. Coding will be performed using the current version of the Medical Dictionary for Regulatory Activities (MedDRA Version 21.0 or higher). Listings will also be provided for the SAF.

Notes:

- Toxicity grade will be coded according to National Cancer Institute (NCI) Common Terminology Criteria for Adverse Events (CTCAE) V4.03 or higher.
- Medical history is defined as records in the “Medical History and Current Medical Conditions”- eCRF form which are not ongoing at Cycle 1 Day 1.
- Current medical conditions are defined as records in the “Medical History and Current Medical Conditions”- eCRF form which are ongoing at Cycle 1 Day 1.

8.6.2 DLBCL-specific medical history and diagnosis

Data on the diagnosis of DLBCL will be presented in a summary table and in listings (SAF). The table will include a summary of the following:

- Stage at screening and initial diagnosis.
- Ann Arbor Disease Stage dichotomized (I and II vs. III and IV).
- Disease risk (IPI) at screening by category (0, 1, 2, 3, 4, 5).
- Disease risk (IPI) at screening (dichotomized: low risk and low-intermediate risk vs. intermediate-high risk and high risk).
- Time since initial diagnosis of DLBCL.
- Bulky disease (present vs. absent) at screening (defined as having a longest lesion diameter of ≥ 7.5 cm as assessed by central radiological assessment).
- Time since first progression/relapse.
- Time since last progression/relapse.
- NHL subtype as per central pathology (DLBCL, Follicular Lymphoma, Mantle Cell Lymphoma etc.).
- Lactate dehydrogenase (LDH) levels at baseline (elevated vs. not elevated).
- Time since discontinuation of last prior anti-DLBCL medication or ASCT [months].

**STATISTICAL ANALYSIS PLAN**MorphoSys AG
MOR208C203

-
- Relapse after initial diagnosis (relapse ≤ 12 months after initial DLBCL diagnosis vs. relapse > 12 months after initial DLBCL diagnosis)

The results of the central pathology have been reviewed by Morphosys and been classified for the tabulation into NHL subtypes. For the subgroup analysis based on dichotomized NHL pathology results the patients with the following diagnoses have been classified further as non-DLBCL patients:

- MARGINAL ZONE LYMPHOMA
- FOLLICULAR LYMPHOMA, GRADE 2
- MANTLE CELL LYMPHOMA, CLASSIC TYPE
- FOLLICULAR LYMPHOMA (GRADE 2 + 3A)

The event times (in months) are defined as (for example):

$[(\text{reference start date}) - (\text{date of initial diagnosis of DLBCL})] / 30.4375$

A listing of the recorded diagnostic lymph node biopsy will also be presented depicting the information on the Diagnostic Lymph Node Biopsy eCRF page. Another listing will show information on NHL subtype as determined by central pathology (the pathological description of the sample as well as the NHL entity used for tabulation).

Data on bone marrow aspiration and biopsies as recorded throughout the study will be summarized in a table and also listed. The data table will summarize the following information on:

- Potential complete response.
- Type of examination.
- Percentage of lymphocytes.
- Type of infiltration.
- Identification of indolent lymphoma in the bone marrow.
- Degree of lymphoma involvement.

Disease involvement assessment of the spleen/liver may occur as part of the full or limited physical examinations throughout the study and recorded data will be presented in a listing.

1.1.1 Handling of incomplete dates regarding DLBCL-specific medical history

If the 'Date of initial diagnosis of DLBCL' is only partially completed, the 'Time since first DLBCL diagnosis' will be calculated based on the following imputation rules:

Table 4: Imputation rules for the 'Date of initial diagnosis of DLBCL'

Component of the Date			Variable
DD	MMM	YYYY	Date of initial diagnosis of DLBCL
✓	✓	✓	No imputation
x	✓	✓	Day 15 of the month
x	x	✓	No imputation
x	x	x	

If the 'Date of initial diagnosis of DLBCL' cannot be imputed, the 'Time since first DLBCL diagnosis' will be considered as 'Unknown'.

If the 'Date of progression/relapse' is missing, the 'Time since first/last progression/relapse' will be calculated based on the following imputation rules:

Table 5: Imputation rules for the 'Date of progression/relapse'

Component of the Date			Variable
DD	MMM	YYYY	Date of progression/relapse
✓	✓	✓	No imputation
x	✓	✓	First day of the month
x	x	✓	No imputation
x	x	x	

If the 'Date of progression/relapse' cannot be imputed, the 'time since first/last progression/relapse' will be considered as 'Unknown'.

2.1.1 Calculation of the International Prognostic Index (IPI):

The IPI is being calculated from the following items based on the information collected on the eCRF page 'Ann Arbor Disease Staging and Disease Risk Assessment':

- Age older than 60 years.
- Lactate dehydrogenase level higher than upper limit of normal.
- ECOG performance status score of 2 or greater.
- Stage III or IV disease.
- More than one involved extranodal disease site.

The IPI gives one point for each of the above characteristics, for a total score ranging from zero to five correlating with the following risk groups:

- Low risk: 0–1 point.
- Low-intermediate risk: 2 points.
- High-intermediate risk: 3 points.
- High risk: 4–5 points.

The categories above will also be collapsed into *low risk* (0–2 points) and *high risk* (3–5 points).

8.6.3 Reason for ASCT ineligibility

The reason for ASCT ineligibility as collected in the eCRF will be listed using the SAF. Additionally, the following three categories will be defined for a table summarizing the number of patients who are ASCT ineligible due to the following reasons (see also Table 6):

- **Chemorefractory:**
 - Chemorefractory patients as indicated on the eCRF page 'ASCT Ineligibility Criteria' ('Failure to achieve PR or CR with salvage therapy').
 - Patients who underwent a stem cell transplantation before as indicated on the eCRF page 'Prior Cancer Therapies for DLBCL – Autologous Stem Cell Transplants'.
 - The presence or absence of any other reason such as comorbidities or high age will be ignored.
- **High age (in presence of absence of comorbidities):**

STATISTICAL ANALYSIS PLAN

 MorphoSys AG
 MOR208C203

- All patients who are ineligible due to high age as indicated on the eCRF page 'ASCT Ineligibility Criteria' ('Age > 70 years').
- Only those patients will be considered who are not already in the 'Chemorefractory' group.
- Presence or absence of other reasons such as comorbidities will be ignored.
- **Other reasons**
 - All other patients who are not in the categories above will be considered as ASCT ineligible due to other reasons.

Table 6: Reasons for ASCT Ineligibility

Priority	High level category	Reason from eCRF
1	Chemo-refractory	Failure to achieve PR or CR with salvage therapy
		Prior ASCT as indicated in eCRF page 'Prior Cancer Therapies for DLBCL – Autologous Stem Cell Transplants'
2	Age or Comorbidity	Age >70 years
		Diffusion lung capacity for carbon monoxide <50% by pulmonary function test
		Left ventricular ejection fraction <50% by multiple gated acquisition echocardiogram
		Other organ dysfunction or comorbidities precluding the use of HDT/ASCT on the basis of unacceptable risk of treatment
3	Patient refusal or Other	Patient refusal of HDT/ASCT
		Other Reason

8.6.4 History of indolent lymphoma

A listing depicting patients with a history of indolent lymphoma will be generated for the SAF. Entries for 'Condition' on the eCRF page 'Medical History and Current Medical Conditions' will be searched for the following keywords:

- Indolent lymphoma
- Indolent non-hodgkin lymphoma
- Indolent NHL
- Other indolent lymphoma
- Follicular lymphoma
- Follicular non hodgkin's lymphoma
- Marginal zone lymphoma
- Splenic marginal zone lymphoma
- Extranodal marginal zone lymphoma
- MALT
- Mucosa associated lymphoid tissue lymphoma
- Chronic lymphocytic leukemia
- Small lymphocytic lymphoma
- Waldenström macroglobulinemia

The listing will show the verbatim term as entered in the eCRF, but also the MedDRA-coded NHL subtype.

8.7 Prior and concomitant medications and non-drug treatments/procedures

8.7.1 Coding

Prior, concomitant and pre-medications will be recorded and coded using the current WHO Drug Dictionary Enhanced (WHO-DDE) and grouped by Anatomical Therapeutic Chemical (ATC) Level 2 and preferred name classes. Surgical and medical procedures will be coded using MedDRA and summarized by SOC and preferred term.

8.7.2 Definitions

- **Pre-medication:** Medication given prior to MOR00208 infusion to mitigate potential infusion-related reactions. Pre-medication encompasses antipyretics, histamine receptor blockers, glucocorticosteroids, meperidine.
- **Prior medication/non-drug treatment:** If the treatment start and stop dates are both before the start date of study treatment, the medication will be classified as prior medication. Patients will only be counted once for multiple drug use (by preferred drug name).
- **Concomitant medication/non-drug treatment:** If the treatment start date is after start of study treatment the medication will be considered as concomitant medication. Patients will only be counted once for multiple drug use (by preferred drug name). If the medication stop date is incomplete, the following algorithm will apply to exclude the medication from the category *concomitant medication*:
 - If stop day is missing but month is complete, medication will only be excluded from concomitant medication if stop month is before month of treatment start.
 - If stop day and month are missing but year is complete, medication will only be excluded from concomitant medication if stop year is before year of treatment start.
 - If stop date is completely missing, medication will not be excluded.
- **Prior and concomitant medication/non-drug treatment:** Medications with start date before start date of study treatment but ongoing or with stop date after the start of study treatment will be considered both as prior and as concomitant medications. Patients will only be counted once for multiple drug use (by preferred drug name).
- **Duration of response (DoR) to prior anti-DLBCL medication or ASCT (in months):**
(date of assessment of tumour progression – date of assessment of first documented response + 1) / 30.4375.
- **Time since last anti-DLBCL medication/radiation therapy/surgery (in months):**
(first date of study treatment – end of treatment date for last prior anti-DLBCL medication/radiation therapy/surgery) / 30.4375.
- **Time since last ASCT (in months):**
(first date of study treatment – date of procedure) / 30.4375.

8.7.3 Data presentation

Summary tables will be presented for:

-
- Prior medications.
 - Concomitant medications which started before start of study treatment.
 - Concomitant medications which started after start of study treatment.
 - Prior non-drug treatments and procedures.
 - Concomitant Non-Drug Treatments and Procedures Which Started Before Start of Study Treatment.
 - Concomitant Non-Drug Treatments and Procedures Which Started After Start of Study Treatment.

All summaries will be conducted on both the FAS and SAF. Listings will be shown for pre-medication, prior medication, and concomitant medication, and listings for prior and concomitant non-drug treatments/procedures (for the SAF).

8.7.4 DLBCL-specific prior therapies

3.1.1 *Prior therapy procedures*

Prior anti-neoplastic therapies will be summarized:

- Prior anti-DLBCL medications:
 - Patients with at least one prior anti-DLBCL medication.
 - Number of therapy lines (as categorical variable).
 - Time since last prior anti-DLBCL medication.
 - Number of patients with 1 vs. ≥ 2 prior anti-DLBCL medications
- Prior radiation therapy:
 - Patients with at least one prior anti-cancer radiotherapy.
- Prior surgery:
 - Patients with at least one prior anti-cancer Surgery.
- Prior autologous stem cell transplantation (ASCT):
 - Patients with prior autologous stem cell transplantation.
 - Duration of response.
- Duration of response to last prior systemic anti-DLBCL medication or ASCT:
 - The duration of response to the patients' last prior anti-DLBCL medication (in case the last prior therapy was a medication) or ASCT (in case the last prior treatment was an ASCT) will be summarized.

Separate listings will be presented on prior anti-DLBCL medications, radiation therapies, surgeries, and ASCT. Listings on individual DLBCL-specific procedures will include information on:

- The type and date of the initial response.
- The type and date of the best overall response.
- Date of progression.
- Reason for therapy discontinuation.
- Therapy start date.
- Therapy end date.
- The number of cycles.
- Therapy type.
- Medication name.
- Number of the particular therapy line.
- Duration of response (only for anti-DLBCL medication, and prior ASCT).

4.1.1 Handling of incomplete dates regarding prior therapies

Handling of missing values for 'Duration of Response (DoR)' to prior therapies

In case the date of initial response or progression is only partially completed the DoR as entered on the eCRF pages for 'Prior Cancer Therapies for DLBCL-Autologous Stem Cell Transplants' and 'Prior Cancer Therapies for DLBCL Medications' will be used. If the entry for DoR to previous therapy line is missing and the date of initial response or progression is only partially completed the following imputation rules will apply:

Table 7: Imputation rules for the 'Date of initial response' and 'Date of progression/relapse'

Component of the Date			Variable	
DD	MMM	YYYY	Date of initial response	Date of progression/relapse
✓	✓	✓	No imputation	No imputation
x	✓	✓	First day of the month	Last day of the month

x	x	✓	No imputation	No imputation
x	x	x		

The 'Duration of Response' to a particular prior therapy will be considered as 'Unknown' if the dates required for derivation cannot be imputed.

Handling of missing values for the derived variables 'Time since the last prior anti-DLBCL medication/radiation/surgery/ASCT'

A partial completion date for the completion of the last prior therapy will be imputed using the following algorithm for the last regimen:

Table 8: Imputation rules for 'End Date' of last prior anti-DLBCL medication, the 'Date of procedure' (for surgery, radiation, ASCT)

Component of the Date			Variable	
DD	MMM	YYYY	'End Date' of last prior anti-DLBCL medication	Date of procedure (surgery, radiation, ASCT)
✓	✓	✓	No imputation	No imputation
x	✓	✓	Day 15 of the month	Day 15 of the month
x	x	✓	No imputation	No imputation
x	x	x		

The 'Time since last prior anti-DLBCL medication/radiation/surgery/ASCT' will be considered as 'Unknown' if the dates required for derivation cannot be imputed.

5.1.1 Refractoriness to prior therapies

Three subgroups for treatment refractoriness in prior therapy lines will be defined using information on prior anti-DLBCL medications collected in the eCRF.

- Primary refractoriness
- Refractoriness to the last prior treatment line
- Rituximab refractoriness

The number (%) of patients in each of these subgroups will be presented. The information will also be provided in listings (for the SAF). The refractoriness to prior therapies will be derived for the FAS only.

8.7.4.1.1 Primary refractoriness

Primary refractoriness is defined as disease progression in the course of the first line treatment, or showing a response of less than PR (i.e., PD or SD) as best response to the first line treatment, or disease progression within ≤ 6 months from the completion of first-line therapy (i.e., the 'End Date' for the first therapy line as entered on the eCRF page 'Prior Cancer Therapies for DLBCL Medications').

- Only systemic anti-DLBCL medications as entered on the 'Prior Cancer Therapies for DLBCL Medications' eCRF page will be considered as first line treatment
- If the status for 'Primary refractoriness' cannot be determined the patient will be considered as having an "Unknown" status.

8.7.4.1.2 Refractoriness to the last prior treatment line

Refractoriness to the last prior treatment is defined as having less than a PR (i.e., SD or PD) as best overall response to the most recent therapy, progression during the course of treatment, or progression within ≤ 6 months from the completion of the most recent therapy line (i.e., the 'End Date' for the most recent therapy line as entered on the eCRF page 'Prior Cancer Therapies for DLBCL Medications').

- Only systemic anti-DLBCL medications as entered on the 'Prior Cancer Therapies for DLBCL Medications' eCRF page will be considered as last prior treatment.
- If the status for 'Refractoriness to the last prior treatment line' cannot be determined the patient will be considered as having an "Unknown" status.

8.7.4.1.3 Rituximab refractoriness

Rituximab refractoriness is defined as having reached less than a partial response to any rituximab-containing treatment regimen, progression during the course of treatment, or progression within ≤ 6 months from the completion of any rituximab-containing (i.e., the 'End Date' for any rituximab-containing therapy line as entered on the eCRF page 'Prior Cancer Therapies for DLBCL Medications'). If the status for 'Rituximab refractoriness' cannot be determined the patient will be considered as having an "Unknown" status.

8.7.4.1.4 Imputation of missing values required for defining refractoriness subgroups

The '**End Date**' for the first treatment line, or the last prior treatment line or any Rituximab-containing treatment line, will be imputed as follows:

- In case day is missing but month and year are complete, the first day of the month or the starting date of the next treatment, whichever is later will be used.
- In case day and month are missing but year is complete, the date will be considered as missing.
- In case day, month and year are missing, the date will be considered as missing.

The '**Date of progression/relapse**' for a particular therapy line will be imputed as follows:

- In case day is missing but month and year are complete, the last day of the month will be used.
 - In case day and month are missing but year is complete, the date will be considered as missing.
 - In case day, month and year are missing, the date will be considered as missing.
 - If the '**Date of progression/relapse**' is completely missing or cannot be replaced by imputation, the following strategy will be used:
 - If the '**Start Date**' of the subsequent therapy line is present, the '**Start Date**' will be used as a surrogate for the '**Date of progression/relapse**' for the previous line of treatment. If the day for the Start Date missing, the day will be imputed using the last day of the month.
 - If the '**Start Date**' of the subsequent therapy line is missing, but the '**End Date**' of the subsequent therapy line is present the '**End Date**' will be used as a surrogate for the '**Date of progression/relapse**' for the treatment line of interest (the patient will be considered as 'refractory'). If the day for the '**End Date**' missing, the day will be imputed using the last day of the month.
- NOTE:** The '**End Date**' of the subsequent therapy will only be used as a surrogate if the time interval between the '**End Date**' of the subsequent line and the '**End Date**' of the previous line is ≤ 6 months (the patient will be considered 'refractory'). Otherwise the refractory status will be considered as 'Unknown'.
- If L-MIND constitutes the immediate treatment line after the line of interest the '**Informed Consent**' date as entered on the '**Informed Consent**' eCRF page will be used.

Table 9: Overview of imputation rules for 'End Date' and 'Date of progression/relapse' for the therapy line of interest

Component of the Date			Variable	
DD	MMM	YYYY	'End Date' for the treatment line of interest	'Date of progression/relapse' for the treatment line of interest
✓	✓	✓	No imputation	No imputation
x	✓	✓	1 st day of the month	Last day of the month
x	x	✓	No imputation	
 1. 'Start Date' of the subsequent treatment (a partially completed date can be imputed as outlined in 2. Table 10) 3. 'Stop Date' of the subsequent treatment if the 'Stop Date' is ≤ 6 months after the 'End Date' of the therapy line of interest (a partially completed date can be imputed as outlined in 4. Table 10) 5. 'Informed Consent' date for L-MIND study participation if the subsequent treatment is L-MIND
x	x	x		

Table 10: Overview of imputation rules for a partially completed 'Start Date' or 'End Date' for the therapy line subsequent to the therapy line of interest (if the 'Date of progression/relapse' for the therapy line of interest has to be imputed)

Component of the Date			Variable	
DD	MMM	YYYY	'Start Date'	'End Date'
✓	✓	✓	No imputation	No imputation
x	✓	✓	Last day of the month	Last day of the month

STATISTICAL ANALYSIS PLAN

 MorphoSys AG
 MOR208C203

x	x	✓	No imputation	No imputation
x	x	X		

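### SAP 8.7.4.1.4 and its Table 9 impute a partial End Date differently, and the text version normally classes a late relapser as refractory

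*SAP*

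**What the plan says.** SAP 8.7.4.1.1 to 8.7.4.1.3 define primary, last-line and rituximab refractoriness. Each is met by a best response below PR, by progression during the line, or by progression within six months of its End Date. For the first line the wording is "Primary refractoriness is defined as disease progression in the course of the first line treatment" and "disease progression within ≤ 6 months from the completion of first-line therapy"; for the last prior line it is "progression within ≤ 6 months from the completion of the most recent therapy line".

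SAP 8.7.4.1.4 covers missing dates. For an End Date with month and year known but no day, the text uses "the first day of the month or the starting date of the next treatment, whichever is later will be used". Table 9, which summarises the same rules, has "1 st day of the month" for that case and does not mention the next treatment.

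For the progression date the section is consistent: "In case day is missing but month and year are complete, the last day of the month will be used". If that date is wholly missing or cannot be imputed, the next line's Start Date "will be used as a surrogate for the" progression date. If L-MIND is the next line, the informed consent date is used instead.

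**The concern.** A next line of therapy normally begins after the earlier line has ended and after the patient has relapsed. Taking the later of two dates, one of which is that start, will normally select it. The earlier line is then deemed to have ended on or after the relapse, the relapse counts as progression during treatment, and the six-month test no longer discriminates.

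The derived status is used in:

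- the baseline table (SAP 8.5);
- the PFS, ORR, DoR and OS subgroups (SAP 11.4) and the centrally confirmed DLBCL subgroups (20.6.2);
- swimmer plots (16.5.9, 17.3);
- forest plots (16.5.6, 18.1, 20.6.2, 20.8.2, 20.8.3, 23.1.2).

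SAP 20.8.3 also reports ORR and DoR for primary refractory DLBCL patients alone. Primary refractory disease is exclusion criterion 1b in Protocol 5.4.2, so that group should be small, and a few false entries could shift its estimates. A false entry would also look like an ineligible patient.

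**Working it through.** The plan states no figure to reproduce. The check applies both rules to constructed dates.

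**Inputs.**
- Text rule (SAP 8.7.4.1.4): E = later of (first of month, next treatment start).
- Table 9 rule: E = first of month.
- Gap in months = (progression date - E) / 30.4375, with the month length from SAP 6.6.
- Refractory on timing if the gap is 6 or less; a gap of 0 or less means on treatment.
- The dates are assumptions.

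**General step.** Let R be the relapse date and N the next treatment's start. If R is on or before N, then under the text E is at least N, so R - E is 0 or negative however long the remission lasted. Under Table 9 the gap equals the true gap plus the days from the first of the month to the true end.

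**Cases** (true end 20 Mar 2014, day not recorded):

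| Case | Progression | Next start | True gap | Text gap | Table 9 gap |
|---|---|---|---|---|---|
| A | 18 Mar 2016 | 11 Apr 2016 | 24.0 | -0.8, refractory | 24.6, not |
| B | 18 Dec 2014 | 12 Jan 2015 | 9.0 | -0.8, refractory | 9.6, not |
| C | missing; surrogate 11 Apr 2016 | 11 Apr 2016 | 24.7 (to surrogate) | 0.0, refractory | 25.4, not |
| D | 18 Mar 2016 | unknown | 24.0 | 24.6, not | 24.6, not |
| E | Mar 2016, imputed 31 Mar | 21 Mar 2016 | 24.4 (to imputed date) | 0.3, refractory | 25.0, not |

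Case A in full: under the text, E is 11 Apr 2016 and the relapse falls 24 days earlier, so -24 / 30.4375 = -0.8. Under Table 9, E is 1 Mar 2014, so 748 / 30.4375 = 24.6. The truth is 729 / 30.4375 = 24.0.

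In C the surrogate and the imputed End Date are the same day. In D the rule does nothing because there is no next start to select. In E the patient enters through the six-month window instead of the on-treatment limb, but is still wrongly refractory.

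**Grid.** True end day 1 to 28, relapse 7 to 60 months later, next treatment 0 to 90 days after relapse in steps of 5 gives 28 x 54 x 19 = 28,728 late relapses. The text rule classes all of them as progressing on treatment; Table 9 classes none as refractory.

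**Cost of Table 9's rule.** Six months is 182.6 days, so true progression on days 1 to 182 with end day 1 to 28 gives 28 x 182 = 5,096 combinations. Moving the end to the first of the month adds 0 to 27 days, which pushes 0 + 1 + ... + 27 = 378 of them (7.4%) past six months. All lie near the limit.

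**The case against.** The best defence is that Table 9 sits in the same section and gives a sound rule. If the programmers followed it, nobody is misclassified by the text. The rest of the section points that way. Progression is imputed to the end of the month, and Table 11 in SAP 8.7.5 uses the same early-start, late-relapse pattern. The progression surrogate would be pointless if the End Date were normally that same date. The sentence may be a slip for the start of the same line, or for the earlier of the two dates; the documents do not settle which.

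The scope is also narrower than it first appears. Patients with less than a PR, or with true progression on treatment or within six months, are refractory anyway. The last prior line has no later prior therapy, so the rule acts there only if L-MIND is the next treatment. The section treats L-MIND as the next line for the progression surrogate but does not say so for the End Date. In a patient with one prior line, the first line is also the last, so the same doubt reaches primary refractoriness.

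All of this stands, and it limits the size of the point. It does not remove the conflict: the text states a rule that gives a wrong result, and nothing available gives Table 9 precedence.

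**Conclusion.** The point holds as an internal contradiction, one side of which is wrong as written. Under the text rule, a patient whose End Date lacks a day, whose next treatment start is known, and who truly relapsed more than six months after the line ended is normally classed as refractory. This clearly reaches primary and rituximab refractoriness in patients with at least two prior lines. For the last or only prior line it is conditional on L-MIND counting as the next treatment.

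Three stronger readings are tempting and are not supported:

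- **That misclassification is certain.** It depends on which rule was programmed, on a known next start, and on the patient not being refractory for another reason.
- **That a count can be given.** If 5% to 20% of about 80 patients had a partial End Date (an assumption), 4 to 16 would have one. That is a ceiling under the assumed rate, before removing those otherwise refractory, those with no known next start and those with a single prior line. The documents give no actual rate.
- **That the trial's results are flattered.** The primary ORR and the main DCR, PFS, DoR, OS, TTP and TTNT analyses do not use refractoriness. If a long prior remission predicts a better outcome, refractory-subgroup results would look better, but that premise is an inference. False primary-refractory labels would also count against the trial, by making enrolled patients look ineligible.

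This should be corrected before the refractory subgroups are interpreted. It does not threaten the primary analysis.

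**What to change.** In SAP 8.7.4.1.4, replace the End Date sentence with Table 9's rule, the first day of the month, and delete the reference to the next treatment's start. As an optional safeguard that is not in Table 9, use the same line's own start date when that is later, so that a line cannot end before it began.

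Confirm which rule was programmed. State how many patients have a partial End Date on a relevant line. If the text rule was used, rerun the derivation and the outputs that depend on it.

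The cost is one sentence and one derivation, plus any reruns; the refractory count may fall. The small downside is that first-of-month imputation lengthens the gap by up to a month, so a few true progressions near the six-month limit become not refractory.
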